1.1.2. Treatment of CIDP and course of the disease

The spontaneous evolution of the disease in the absence of any therapy has not been well described in the literature. The effectiveness of treatment with corticosteroids was shown when chronic polyradiculoneuropathy was first described by Austin in 1958 [8].

Three therapeutic options have proved to be efficacious in CIDP: IVIg, oral corticosteroids and plasma exchange. The EFNS/PNS guideline recommends the use of IVIg or corticosteroids as first line treatment. Plasma exchange, which is less widely available and less tolerated, is only recommended as an alternative in case IVIg and corticosteroids are inadequate. The American Academy of Neurology considers that IVIg should be offered for the long-term treatment of CIDP (Level A recommendation) [9].

Regarding IVIg, a meta-analysis in a Cochrane review of 5 double blind placebo-controlled randomised trials showed that a significantly higher proportion of patients improved in disability within one month after IVIg treatment compared with placebo [10]. Only one study (ICE study) had a long-term follow-up; in this study, 57 responder patients were re-randomised for an extension 24 - week phase between either IVIg at 1 g/kg or placebo every 3 weeks. The percentage of relapse was 13% with the IVIg and 45% with the placebo (p=0.011) [11].

1.2. Target

The specific mechanism of action of IVIg in CIDP is not understood. However, studies in other diseases treated with IVIg have demonstrated that IVIg may inhibit autoantibody production, neutralize pathogenic antibodies, and decrease antibody-dependent cellular cytotoxicity by blocking Fc-receptors (FcγR) on macrophages [12] and upregulate inhibitory Fcγ receptor FcγRIIB on B cells [13]. Furthermore, peripheral blood from participants treated with IVIg shows increased CD8-positive suppressor T-cell function.

The B-cell activating factor BAFF contributes to B-cell homeostasis and (auto-) antibody production. BAFF was recently identified as one key molecule in the development of autoimmune diseases and acts by down-regulation in CIDP. In 2013 Bick et al identified BAFF as a new target for IVIg in CIDP treatment and provide a new FcγR independent, mechanism of action for IVIg.

1.3. Non-Clinical and Clinical Information

The study drug is I10E, a ready-to-use liquid human normal immunoglobulin preparation for IV administration (ATC Code: J06BA02). I10E is manufactured by LFB BIOMEDICAMENTS (see Section 6.1.1 Description of study drug).

Marketing Authorization Application (MAA) was submitted in Intravenous Immunoglobulin (IVIg) Core Summary of Product Characteristics (SPC) indications through the Decentralized Procedure (DCP) in the following European Union Member States: Austria, Belgium, Czech Republic, Denmark, Finland, Germany, Greece, Hungary, Italy, Luxembourg, the Netherlands, Spain, Slovakia, Sweden, and the United Kingdom. The first national marketing authorization was granted in the United Kingdom in August 2015, then in Denmark, Germany, Hungary, Belgium and Finland.

I10E MAA dossier was also submitted in Mexico and approved in April 2015 in the core SPC indications, multifocal motor neuropathy and Birdshot retinochoroidopathy.

This section summarises the available clinical and non-clinical data of I10E.

1.3.1. Non-clinical data

I10E meets specifications of the European Pharmacopoeia Monograph 0918 on IVIg. Non-clinical safety studies of I10E were performed in accordance with Good Laboratory Practice. For more information, refer to the Investigator's Brochure.

1.3.2. Clinical data

As of 08 October 2015, 107 patients have been treated with I10E in open-label clinical studies: 62 patients with primary immune deficiency (PID) in study I10E-0718 (completed), 38 patients with immune thrombocytopenia (ITP) in study I10E-0719 (completed) and 7 patients with chronic inflammatory demyelinating polyneuropathy (CIDP) in an ongoing single-arm study I10E-1302 (PRISM study). In addition, 22 patients with multifocal motor neuropathy (MMN) have been enrolled in an ongoing double-blind cross-over randomized study I10E-0901 (LIME study) and at least 17 of them were administered with I10E.

In PID patients, a total of 766 infusions at a dose ranging from 0.22 to 0.97 g/kg were administered. I10E has proved to be effective in preventing serious bacterial infections (SBIs) with an annual SBI rate below the EMA/FDA requirement of <1/patient. I10E exhibited a PK profile comparable to those of other IVIGs with a mean terminal half-life of 33.6 days.

In chronic primary ITP patients, a total of 73 infusions were administered at a median dose of 1.0 g/kg on one day, 70 of them being administered on 2 consecutive days. I10E was effective in increasing rapidly the platelet count and reducing and preventing bleedings with a response rate of 63.2% of patients using the stringent definition of response of the revised EMA guideline on the clinical investigation of IVIG and 83.8% using the primary efficacy endpoint of the previous EMA guideline.

Monitoring of adverse events (AEs), vital signs, ECG and laboratory parameters showed a safety profile comparable to that of other IVIG in patients with PID or chronic ITP.

In MMN patients, the ongoing study I10E-0901 (LIME study) compares I10E to Kiovig[®] maintenance therapy at a dose of 1.0 g/kg every 4 weeks up to 2.0 g/kg every 4 to 8 weeks for approximately one year. The enrolment in the study is completed.

In CIDP patients, the study I10E-1302 (PRISM study) aims at evaluating the safety and efficacy of one dose of 2.0 g/kg of I10E followed by 7 doses of 1.0 g/kg every 3 weeks. A total of 42 patients are planned to be enrolled in the study.

As of 08 October 2015, no serious adverse reactions were reported in both study I10E-0901 and study I10E-1302.

An extension of study I10E-1302, namely study I10E-1306 (PRISM-2 study) has been initiated to assess the efficacy and safety of a reduced maintenance dose of I10E in responder patients at the end of study I10E-1302. For more information, refer to the Investigator's Brochure.

I10E dose regimen required in this protocol is already commonly used in treatment of CIDP with IVIG and has shown a favourable benefit to risk ratio. The dose of I10E recommended in this protocol will not exceed the doses used in current practice in patients with CIDP as well as in other indications of immunomodulation.

This section is not intended to be all inclusive regarding risks and benefits. The investigator must become familiar with all sections of the I10E Clinical Investigator's Brochure.

1.4. Rationale of the study

LFB BIOTECHNOLOGIES wishes to develop I10E for the CIDP indication. As required by the European Guideline EMA/CHMP/BPWP/94038/2007 rev.4 [14], confirmatory data of I10E in CIDP should be provided to Health Authorities in order to get registered in this indication. Published literature already indicates a beneficial effect of IVIg in CIDP.

The objective of this study is to provide confirmatory data on the efficacy and safety of I10E in the initial and maintenance treatment phases of CIDP. In Ig-naive patients and in patients with a relapse after withdrawal of Ig treatment, an improvement of the neurological status is expected with I10E. The study will include both types of CIDP patients.

Two main studies named “ICE” and “PRIMA” have already proven the efficacy and safety of Gamunex[®] (IVIg 10% from Talecris Biotherapeutics, NC, USA) and Privigen[®] (IVIg 10% from CSL Behring GmbH) respectively.

Study design, primary endpoint and patient selection criteria in this study have been chosen as close as possible to the previous studies (ICE and PRIMA), in particular to “PRIMA” study as it was validated by EMA via a scientific advice (Privigen[®] EPAR EMA/CHMP/749630/2012).

CIDP patients either Ig-naive or relapsing after Ig treatment withdrawal for at least 3 months will be screened and enrolled. They will receive I10E at a dose of 2g/kg during the first course, then a dose of 1g/kg every 3 weeks during 7 following courses. The treatment and follow-up period will be 24 weeks, as recommended by the EFNS/PNS guideline [4].

The primary endpoint will be the responder rate at the EOS visit. Responders are defined as patients with a decrease ≥ 1 point in the adjusted INCAT disability score between baseline and the EOS visit.

1.4.1. Disability and impairment scales

In 2013, Els K. Vanhoutte, Catherina G. Faber and Ingemar S.J. Merkies [40] published outcome measures in inflammatory peripheral neuropathies on behalf of the PeriNomS study group the 196th ENMC international workshop. Their recommendations on the best scales for CIDP have been included in the current protocol. The following scales will therefore be assessed at 12 weeks and EOS visit as part of secondary endpoints:

- Adjusted INCAT disability score;
- Grip strength with the Martin vigorimeter in both hands, Rasch-built Overall Disability Scale (R-ODS);
- Patient and Investigator Clinical Global Impression (CGI): Severity (CGI-S), Efficacy (CGI-E) and Improvement (CGI-I);
- Medical Research Council (MRC) 12 muscles sum score (0 to 5) and Rasch-modified MRC (0 to 3);
- Original INCAT disability score.

1.4.2. Immunological background and research of biomarkers

The pathogenesis of CIDP is not fully understood. T cells, B cells, macrophages, cytokines and chemokines, autoantibodies and complement are the main effectors involved in the pathogenesis of CIDP and are therefore the main target of therapies. Immune cells and soluble mediators are

regulated by IVIg and this regulation is correlated in many instances with IVIg response. Numerous biomarkers have been proposed in CIDP but none seems to predict the response to IVIg accurately. This trial gives the opportunity to assess specific biomarkers, their modulation by IVIg treatment and their correlation with clinical response.

IVIg seems to work by a direct competition and quantitative blockade of autoantibody action by different mechanisms.

In 2013 [name] highlighted IgG4 anti-contactin1 (CNTN1) and anti-neurofascin (NF155) autoantibodies as poor prognostic factors after IVIg therapy: in her series, the presence of at least one of these autoantibodies identified a lack of response to IVIg [15]. Anti-CNTN1 and anti-NF155 antibodies were associated to small subgroups of CIDP patients with specific phenotypic features.

The concept of an aberrant B cell response as a pathogenic part of CIDP is widely accepted. IgG mediated effector functions require the interaction with their Fc γ R on effector cells. The type II Fc γ RIIB (CD32B) is the only inhibitory Fc γ R and is expressed on circulating monocytes and B cells. On B cells, signalling through this receptor inhibits transformation of B cells into antibody secreting plasma cells [16]. Recent works has shown that this receptor is modulated by IVIg in CIDP patients [17] [18] [19].

The immune status of patients as well as their modulation by a high dose of IVIg (2g/kg) will be documented by monitoring the expression of the Fc γ RIIB B cell marker in blood.

Other soluble biomarkers such as (BAFF) contribute to B-cell homeostasis and autoantibody production [20].

Complement components have been shown to be modulated by IVIg [21] [22]. Scavenging of complement fragments is a mechanism believed to be important in the efficacy of IVIg. Binding of IgG molecules to potentially harmful complement fragments (C3b, C4b) blocks deposition of these fragments onto their target and the formation of amplification convertases, decreasing activation of C5 and deposition of the C5b-C9 membrane attack complex.

The modulation of the complement pathway following IVIg treatment can be monitored by the combined dosage of CH50 (ELISA-based assay) for the quantitative determination of functional classical, mannose binding lectin and alternative complement pathways, and the quantitative dosage of C3 and C4 proteins (routinely performed by nephelometry) in serum samples.

Serum concentrations of these markers in samples will be measured in order to document their modulation at both high (2g/kg) and low (1g/kg) doses of IVIg and to assess whether the modulation is dose dependent.

Analyses of these biomarkers should advance understanding of immune modulation and mechanism of action of IVIg in CIDP.

1.4.3. Neurophysiological examination (Ancillary study; Italian sites only)

Monolateral nerve conduction studies (NCS) will be performed through the following minimum neurophysiological protocol. Local laboratory standards will be employed.

Motor nerve conduction studies will be performed in the following nerves:

- median nerve: the motor response will be recorded with surface electrodes over the abductor pollicis brevis muscle and the sites of stimulation will be at the wrist (1 cm proximal volar wrist fold) and at the elbow;
- ulnar nerve: the motor response will be recorded with surface electrodes over the abductor digiti minimi muscle and the stimulation site will be at the wrist, above and below elbow (3 cm above and below elbow) and axilla;
- deep fibular nerve: the motor response will be recorded with surface electrodes over the extensor digitorum communis and the sites of stimulation will be proximal to the anterior tarsal tunnel, 2 cm distal the proximal margin of fibular head and in the popliteal fossa.

Motor nerve conduction velocities, distal latencies, and amplitude of the negative phase of compound muscle action potentials will be measured.

F wave studies will be performed in the ulnar nerve with measurement of mean F latency and frequency of F response.

Sensory nerve conduction studies:

- orthodromic sensory NCS of the median nerve will be recorded at the wrist and the stimulation with ring electrodes will be at digit III;
- orthodromic sensory NCS of the ulnar nerve will be recorded at the wrist and the stimulation with ring electrodes will be at digit V;
- antidromic sensory NCS of the sural nerve will be recorded at posterior-lateral malleolus and the site of stimulation will be at the posterior-distal leg with the cathode at 12 cm from the active electrode.

As methods differ from site to site, all participating centers must provide complete information on their laboratory's standard NCS protocols.

If clinically indicated, additional studies may be performed at the discretion of the examiner.

1.4.4. Peripheral nerve ultrasonography (Ancillary study; Italian sites only)

High-resolution ultrasound (USG) of peripheral nerves is a valuable complement to neurophysiology especially in the work-out of mononeuropathies. Less is known on polyneuropathies, where the great heterogeneity made difficult the identification of a specific alteration pattern. In previous studies in CIDP patients, nerve USG showed diffuse enlargement of cross sectional area (CSA) of peripheral nerves trunks and cervical roots [23] [24] [25] [26] [27].

Recently, USG findings in CIDP have been shown not only to contribute to the diagnosis, but also to mirror the underlying pathophysiological mechanisms. Nerve enlargement was statistically related to disability and muscle strength, and the relationship between duration of symptoms and USG classes was highly significant [28].

For the nerve USG evaluation, USG systems equipped with medium (the lowest being around 6 Hz) and high-frequency (15-18 MHz) broadband probes will be used. USG will be performed in the neurophysiologically evaluated side. Additional nerves may be evaluated at the discretion of the examiner.

Nerve assessment required and pre-determined site of measurements are:

- Median: wrist, mid-forearm, elbow, mid-humerus and axilla

- Ulnar: wrist, mid-forearm, elbow, mid-humerus and axilla
- Fibular: fibular head and popliteal fossa
- Sural: median third of the leg

Optional assessments (for skilled USG operators) are:

- Supraclavicular brachial plexus (strongly suggested)
- Radial at humeral sulcus
- Posterior interosseus nerve under the supinator muscle
- C5-C6-C7 cervical roots.

USG outcome measures will be:

- 1) Maximal/minimal CSA for each nerve along the visible course;
- 2) Intra-nerve and inter-nerve variability;
- 3) USG immune-related classification.

1. Maximal and minimal CSA.

The method to calculate CSA (just inside the hyperechoic rim of the nerve in transversal section) is usually the “ellipse method” when applicable (when the nerve in the transverse scan has an elliptical or roundish shape) or the “tracing method” when the nerve has an “irregular” shape. Echogenicity alteration not associated with CSA alteration will be not considered.

In addition to the pre-determined sites of imaging, maximal (MAX-CSA) and minimal (MIN-CSA) CSA enlargement along the visible course will be recorded for each nerve.

The CSA of whole plexus will be bilaterally measured. Moreover, after identification of the cervical spinal root level, CSA of each root (from C5 to C7) are measured just before entering the spine [29].

Each centre will use its own previously established CSA normative values. Every participating centre has to submit their normative values in advance. If not available, normative values adopted in the coordinating site will be used.

2. Intra- and inter-nerve variability

"Intra-nerve CSA variability" (for each nerve: maximal CSA/minimal CSA) and "inter-nerve CSA variability" (for each patient: maximal intra-nerve CSA variability/minimal intra-nerve CSA variability) will be evaluated [30] [31]. Intra-nerve variability will be evaluated only in ulnar, median and fibular nerves, having sural nerve a very short assessable segment (with only a single measure taken).

Normal values of upper cut-off of intra-nerve ratio are for median nerve 2.3 and for the ulnar nerve 2.1. Concerning inter-nerve variability the upper cut-off value is 1.9.

3. USG immune-related classification

On the basis of previous USG observations [28] USG pattern is classified as follows:

Class 1: large nerves, with hypoechoic segments and increased nerve CSA. Enlarged fascicles may be seen or the nerve may appear enlarged and hypoechoic without fascicular structure.

Class 2: large nerve, with segments with increased nerve CSA and coexistence of hyper and hypoechogenic enlarged (or normal) fascicles (in other words, in the same point we observe fascicles with hyperechoic and other fascicles with hypoechoic structure).

Class 3: normal nerve size, but changes in echogenicity (nerve appears hyperechoic with reduced CSA). The edge of the nerve and surrounding is not clear. The hyperechoic rim of epineurium is not clearly identified. Fascicles are not well visualized.

Only CIDP patients enrolled in Italian centres will undergo USG examination coupled with neurophysiology, as Italian sites already have nerve examination-trained ultra-sonographers.

2. STUDY OBJECTIVES

2.1. Primary objective

To assess the efficacy of I10E in improving the disability of patients with CIDP.

2.2. Secondary objective

To assess the safety of I10E in patients with CIDP.

2.3. Exploratory objectives

- To assess a potential relationship between serum total IgG trough levels, biomarkers levels and clinical response – as assessed by neurological scales – in patients with CIDP.
- To assess a potential relationship between USG coupled to neurophysiology analysis of nerves and clinical response – as assessed by neurological scales – in patients with CIDP (ancillary study in Italy).

3. STUDY DESIGN

Study design is outlined in [Figure 8-1](#).

3.1. Design and study periods

This is a phase III, international, multicentre, single-arm, open-label, prospective study.

Study periods are as follows:

3.1.1. Screening

The screening period goes from signature of informed consent to first study drug administration. The screening biological tests should be performed and their results checked by the Investigator within a period of 4 weeks before first study drug administration.

The exclusion and inclusion criteria (except those related to screening biological assessments) will be verified prior to screening. The screening biological test results will be verified before the first study drug administration.

The screening period shall not exceed 4 weeks.

3.1.2. Baseline

Baseline data are those obtained during the screening period before first study drug administration. If multiple results are available for a given assessment, the most recent will be considered.

3.1.3. Inclusion

A patient is considered included once he/she receives the first study drug administration.

3.1.4. Treatment

Patients who meet all the eligibility criteria will receive one dose of study drug at 2 g/kg over 2 to 5 days. Three (3) weeks later, they will start to receive 7 doses of study drug at 1 g/kg over 1 to 2 day(s) each, every 3 weeks (+/- 7 days).

Investigators or Study Nurses will call patients 4 days (+/-1 day) after the end of each study treatment course to document potential AEs and TAAEs (see Section [8.2.4](#)).

Duration of the treatment period will be approximately 21 weeks.

3.1.5. Follow-up and End of study

A follow-up visit will occur 3 weeks +/- 7 days after the last study drug administration. At the end of the follow-up period, patients will undergo an EOS visit. This visit occurs 3 weeks after the 8th course of study drug. In the event of premature discontinuation from the study drug or patient withdrawal from the study, an EOS visit is performed within 7 days and prior to administration of any other treatment for CIDP (See Section [8.2.7](#)). The reason for premature study drug discontinuation / study withdrawal should be accurately assessed and entered into the eCRF.

The total duration of the study for a patient is approximately 24 to 29 weeks.

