8.2.7. Visit 11: Week 24 (+/- 7 days) - End of study visit

At the end of the 24-week treatment and follow-up period, patients undergo an end of study visit evaluation. This visit occurs 3 weeks after the 7th course of study drug at a dose of 1 g/kg.

In the event of premature discontinuation from the study drug or patient withdrawal from the study, an end of study visit is performed within 7 days.

The end of study assessment should be performed before any other treatment including Igs is administered.

The reason for premature study drug discontinuation / study withdrawal should be accurately assessed and entered into the eCRF.

The following study procedures will be carried out:

- Complete physical examination.
- Biometric information: weight.
- Vital signs: temperature, heart rate, systolic and diastolic blood pressure.
- Neurological status assessment:
 - INCAT disability score (adjusted INCAT disability score will be deduced from reported values).
 - Patient and Investigator CGI-S, CGI-E and CGI-I.
 - MRC sum score.
 - Rasch-modified MRC sum score.
 - R-ODS.
 - Grip strength with Martin vigorimeter in both hands.
- Biological tests in local laboratory:
 - Haematology:

- Complete blood count + differentials, Hb, MCV, platelets count.
- Haptoglobin.
- Reticulocytes, direct Coombs test
- Biochemistry:
 - Creatininemia, glomerular filtration rate according to MDRD.
 - LDH.
 - Total and free bilirubin (total bilirubin in all patients; if total bilirubin > ULN, free bilirubin will be assessed from the same blood sample, as total bilirubin).
 - AST, ALT, ALP, γ GT.
 - Total serum protein level.
 - C3 and C4 antigens.
 - Serum total IgG trough levels.
- HBs Ag, anti HBs & anti HBc Ab, HIV, HCV tests.
- Serum reference sample for long term storage.
- Urine protein reagent strip test [to be performed before study drug administration in patients who at screening tested for urine protein reagent strip result "1 cross 1 (+) and/or had GFR in the range of 60-80 mL/min/1.73m²]:

If urine protein reagent strip test result = Negative or Trace	Action: No further urine test required
If urine protein reagent strip test result = 1 cross (1 +) or more	Action: Assess either AER or PER from a 24h-urine collection sampled at least 7 days after the end of the previous study drug course or assess ACR or PCR from a spot urine sample immediately following the urine protein reagent strip test (i.e. urine obtained before study drug administration).

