9.5.3. Adverse Event recording and reporting

Period of (Serious) Adverse Event Data Collection:

In order to ensure complete safety data collection, recording and reporting, all (S)AEs occurring during the study, i.e. after signature of the Informed Consent, must be recorded, even if no study drug was administered. These include all AEs occurring, recurring, or worsening after the signature of the informed consent. The period of observation for the study is from the screening visit to the end of study visit.

If the Investigator becomes aware, after that period, of any unusual safety information or any safety information that appears to be drug related involving a patient who had participated in the study, even after the patient completes the study, he/she should contact the sponsor to determine how it should be documented and reported.

Recording and Description of (Serious) Adverse Event:

All AEs occurring after signature of the informed consent until the end of study visit will be recorded in the appropriate pages of eCRF, including AEs occurring during the screening period and before the first administration of study drug, other than baseline findings which will be recorded as medical history.

Each individual AE is to be listed as a separate entry on the eCRF AE form. The Investigator will provide information on dates of onset and resolution, seriousness, severity, frequency, action(s) taken with regard to corrective therapy or to the study drug, outcome and relationship to the study drug. The Investigator must report to the Sponsor or its designee all AEs that occur during the study from the time the written informed consent is given until the EOS visit or premature termination, regardless of their relationship to the study drug. Apart from AEs clinically observed by the Investigator, the patient will be given the opportunity to report AEs spontaneously. A general prompt will also be given to detect AEs, e.g. "Did you experience any illness or unusual symptom since your last visit?"

Follow-up of Adverse Events:

All AEs and SAEs assessed as not related to study medication, including clinically significant laboratory tests or physical examination findings, must be followed until the event resolves, the condition stabilizes, the event is otherwise explained, or the final study visit occurs, whichever comes first.

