AEs or SAEs assessed as related to study drug will be followed for as long as necessary to adequately evaluate the subject's safety, or until the event stabilizes, or the subject is lost to follow up. If resolved, a resolution date should be provided.

The Investigator is responsible for ensuring that follow-up includes any supplemental investigations indicated to elucidate the nature and/or causality of the AE. This may include additional clinical laboratory testing or investigations, histopathological examinations, or consultation with other health care professionals as is practical.

If a patient is withdrawn from study due to safety reasons, he/she should be followed until the event disappears, is otherwise explained or the patient's condition has stabilised.

Any patient who voluntarily withdraws from the study should be carefully questioned for the possible occurrence of an adverse event. Whenever possible, a patient should be followed through the last scheduled visit.

If no follow-up information can be provided after all efforts and attempts, the Investigator must document the outcome as "unknown" and provide a justification.

9.5.4. Procedures for reporting Serious Adverse Events, Pregnancy and overdose/abuse/misuse.

9.5.4. 1. SAE

The Sponsor or its representative must be informed immediately, and no later than 24 hours, of receipt of the SAE information by the site.

If one or more seriousness criteria is fulfilled, the Investigator must promptly forward to the Sponsor or its representative a duly completed "SERIOUS ADVERSE EVENT NOTIFICATION FORM" provided by the Sponsor, even if the data are incomplete or if it is obvious that more data will be needed in order to draw any conclusions, but as soon as the minimum of following information is present:

- identification of the notifying person,
- identification of the clinical study,
- identification of a patient (patient number and/or initials),
- description of the SAE and relationship to the study drug.

After the initial SAE report, the Investigator is required to proactively follow each patient and to provide further information on the patient's condition. The Investigator will ensure that follow-up includes any further investigations as may be indicated to elucidate the nature or the causality of the SAE.

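### Patients stopped at or soon after an infusion have at most 7 to 10 days in which new adverse events are sought, against 14 to 28 days for completers

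*Protocol*

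**What the plan says.** **Completers.** Protocol section 3.1.5 states: "A follow-up visit will occur 3 weeks +/- 7 days after the last study drug administration". It places the end-of-study (EOS) visit at the end of that period: "This visit occurs 3 weeks after the 8th course of study drug".

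**Early stops.** The same section states: "In the event of premature discontinuation from the study drug or patient withdrawal from the study, an EOS visit is performed within 7 days". Section 8.2.7 repeats the limit: "an end of study visit is performed within 7 days". Both sections want this assessment done before any other CIDP treatment is given.

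**End of AE recording.** Section 9.5.3 states: "The period of observation for the study is from the screening visit to the end of study visit". It also names premature termination as an alternative end of AE reporting. Section 3.2.3 defines the safety endpoints from first administration to the EOS visit.

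**What continues afterwards.**
- Sections 5.4 and 9.5.3 follow an AE that led to withdrawal until it resolves or stabilises, and follow drug-related AEs for as long as is needed.
- If the investigator later learns of unusual or apparently drug-related information, section 9.5.3 has the sponsor contacted to decide how it is documented.
- In the paragraph on voluntary withdrawal, section 9.5.3 adds: "Whenever possible, a patient should be followed through the last scheduled visit".
- Section 11.1.2.5 asks that new AEs be entered after a premature withdrawal, but gives no end date and no contact at which to ask.

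**SAP.** Section 4.7.2 gives treatment-emergent AEs (TEAEs) a start, the first infusion, and no end. Its rates divide events by numbers of patients, courses and infusions. The rate of drug-related TEAEs by course divides by all patients treated at that course.

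**The concern.** The 7-day limit has a sound purpose: it obtains the efficacy assessment before new CIDP treatment confuses it. The same visit also closes active collection of new AEs. The shortening is greatest for patients stopped during or just after an infusion, a group likely to include those stopped for an acute reaction. Length of follow-up then depends on tolerability. Section 9.2.1 names haemolysis, thromboembolism and acute renal failure as important potential risks. An onset in the second or third week after the last infusion would be asked about in a completer and not in such a patient. Safety is the trial's stated secondary objective, 42 patients are planned and section 3.4 sets up no DSMB, so a few shortened records matter to the safety description. The efficacy conclusion does not depend on them.

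**Working it through.** **Inputs**
- Last course at Week 21 and EOS at Week 24 (Protocol 8.2.6 and 8.2.7), with +/- 7 days.
- EOS within 7 days after an early stop (3.1.5, 8.2.7). The 7 days are tied to discontinuation or withdrawal, not to the last infusion.
- New AEs recorded to EOS (3.2.3, 9.5.3).
- Temporally associated AEs (TAAEs): during infusion to 72 hours after it (synopsis).
- Telephone call 4 +/- 1 days after each course (3.1.4).

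**Step 1: the plan's own window.** Week 24 - Week 21 = 3 weeks = 21 days. With +/- 7 days this is 14 to 28 days, which agrees with section 3.1.5.

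**Step 2: early stops.** Let t be the number of days from the last infusion to the decision to stop. EOS then falls between day t and day t + 7.

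| Stop decided on day t | EOS after last infusion | Largest share of 21 days |
|---|---|---|
| 0 | day 0 to 7 | 7/21 = 33% |
| 3 (72 h) | day 3 to 10 | 10/21 = 48% |
| 7 | day 7 to 14 | 14/21 = 67% |
| 14 | day 14 to 21 | 21/21 = 100% |
| 21 (next pre-dose visit) | day 21 to 28 | no shortening |

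The window is certain to be below the completers' minimum of 14 days when t + 7 < 14, that is, when t < 7. It can be below it for any t < 14. For a stop on the infusion day, at least 14/21 = 67% of the nominal window is lost.

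**Step 3: the TAAE window.** An EOS visit on days 0 to 2 would come before the end of the 72-hour TAAE period. A day-4 call is planned after each course, but the documents do not say whether a new event reported in it after an early EOS visit is recorded.

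**Step 4: the rates.** A course cut short on the infusion day adds one full unit to the SAP's course denominator but at most a third of the nominal observation time. SAP 4.7.1 summarises time from first infusion to EOS, but no AE rate uses it.

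**Step 5: possible size.** The documents give no rate of such stops. If 5% to 10% of the 42 patients stopped on an infusion day (assumption), that is 2.1 to 4.2, or about 2 to 4 patients. As an illustration, suppose that all stopped at one course with 42 treated, that each was seen for the full 7 days, and that events were spread evenly over 21 days at one rate for everyone. The observed time is then 42 - 2 x 14/21 = 40.7 to 42 - 4 x 14/21 = 39.3 course-equivalents. That course's rate would be understated by 1.3/42 = 3% to 2.7/42 = 6%. It would be more if the stopped patients had a higher event rate, and less per course if the stops were spread over courses.

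**The case against.** The strongest reply is that these patients are not abandoned. The event that caused the stop, and any drug-related AE, is followed past the EOS visit with supplemental tests if indicated, so a patient stopped for a reaction is probably still in contact with the investigator. Later drug-related information has a route to the sponsor. The early EOS visit includes the haematology, LDH, haptoglobin, bilirubin and creatinine tests, with reticulocytes and direct Coombs. Infusion reactions are concentrated in the 72-hour window, and many stops will be decided at a pre-dose visit. All of this stands, and it limits the size of the problem. It does not close it, because those provisions mainly follow events that already exist, and the route to the sponsor depends on the investigator happening to hear.

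Two passages might seem to close it. The 3-week follow-up visit in section 3.1.5 is worded generally, but the visit list in section 8.2 has no such visit apart from Visit 11, the EOS visit itself. The request to follow a patient through the last scheduled visit stands in the paragraph on voluntary withdrawal, applies only where possible, and leaves open whether the early EOS visit or Week 24 is meant.

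A reader might also infer stronger points that the documents do not support:
- *All AE collection stops at the early visit.* It does not, given sections 5.4, 9.5.3 and 11.1.2.5. The gap concerns active collection of new AEs.
- *The urine rule in section 8.2.7 cannot be met at an early visit.* The rule reads "Assess either AER or PER from a 24h-urine collection sampled at least 7 days after the end of the previous study drug course", but goes on to allow a spot-urine ratio with no 7-day condition, so there is no conflict.
- *Residual drug shows that the lost time carries risk.* The "mean terminal half-life of 33.6 days" in section 1.3.2 comes from patients with primary immune deficiency, and neither document links residual IgG to AE onset.
- *The SAP excludes later events.* It sets no TEAE end date. The limit comes from the protocol's recording rule.

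**Conclusion.** The concern holds for new-onset AEs in patients stopped at or shortly after an infusion: 0 to 7 days for a stop on the infusion day and at most 10 days for a stop at 72 hours, against 14 to 28 days for completers. It does not apply to a stop decided at the next pre-dose visit. Event rates can be understated and the safety profile can look better than it is. The documents do not show that it will, because the number of such stops and the timing of later events are unknown. The number is probably small. The conclusion rests on reading section 9.5.3 as ending the recording of new AEs at the early EOS visit. Sections 9.5.3 and 11.1.2.5 do not say this consistently, and that inconsistency is itself a reason to settle the cut-off. The sample size and the primary test are not affected. The change is worth making because it is cheap and removes a difference in follow-up that depends on tolerability.

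**What to change.** 1. Keep the EOS visit within 7 days of an early stop, before other CIDP treatment, for efficacy.
2. In Protocol 3.1.5, 8.2.7 and 9.5.3, state that new AEs are collected to 3 weeks (+/- 7 days) after the last infusion for every treated patient who consents. Where the EOS visit falls earlier, use a telephone contact modelled on the day-4 call.
3. Give the TEAE definition in SAP 4.7.2 the same end date, and flag events with onset after new CIDP treatment.
4. Reconcile sections 9.5.3 and 11.1.2.5 on whether new AEs after an early EOS visit are recorded and counted, and say which visit is meant by the last scheduled one.
5. At the least, have the SAP report days observed after the last infusion for patients stopped early.

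The cost is one extra call for a few patients and some wording in both documents. Some added events will be confounded by new treatment, hence the flag. A telephone call will still miss events that show only in laboratory tests.
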